8.5.1 PRIMARY EFFICACY ANALYSIS

INO-4800	COVID19-311
Inovio Pharmaceuticals, Inc.	Clinical Protocol

The primary hypothesis of relative efficacy greater than 30% will be tested with H₀: $p \ge 0.70/(0.70+k)$ vs. H₁: p < 0.705/(0.70+k), where p is the true proportion of subjects with disease who receive INO-4800 relative to the total number of subjects with disease, and k is the total amount of follow-up time in the placebo group divided by the total amount of follow-up time in the INO-4800 group.

A p-value for this hypothesis test and corresponding 95% confidence interval will be computed based on the exact binomial method of Clopper-Pearson. Success will be concluded if the one-sided p-value is <0.025 and the corresponding lower bound of the two-sided 95% Cl for efficacy exceeds 30%.

For calculating k, an individual subject's follow-up time is either:

- a) the date of first disease diagnosis date of the start of surveillance period +1 (for subjects who are cases), or
- b) the date of last follow-up date of the start of surveillance period +1 (for subjects who are non-cases).

This methodology is based on the following. Assuming that the number of subjects who are cases in the INO-4800 group follows a Poisson distribution with parameter λ_v and the number of subjects who are cases in the placebo group follows a Poisson distribution with parameter λ_c , then conditional on total number of subjects with cases, t, the number of subjects who are cases in the INO-4800 group follows a binomial distribution with parameters (t, p= $\lambda v/(\lambda v+\lambda c)$). The relationship between p and efficacy is: efficacy = (1-(1+k)p)/(1-p). Therefore, testing efficacy > 30% corresponds to testing p < 0.70/(0.70+k). Similarly, the confidence interval for efficacy is (1-(1+k)UB_p)/(1-UB_p), (1-(1+k)LB_p)/(1-LB_p), where UB and LB are the Clopper-Pearson upper and lower limits for the proportion.

The efficacy time frame is defined by symptoms beginning at any time starting from 14 days after Dose 2 and ending 12 months after Dose 2. Subjects identified as cases that started prior to this time point will be excluded. Subjects with multiple instances meeting the case definition will be counted only once, using the first such instance.

The PP population will be primary for the analysis of efficacy in this trial. Efficacy analysis using the mITT population will also be conducted counting cases from 14 days postdose 1 as a supportive analysis. The ITT population will also be used for a supportive analysis counting cases starting from randomization.

8.5.2 SECONDARY ANALYSES

8.5.2.1 Efficacy

The secondary efficacy incidence endpoints will be analyzed in the same manner as the primary hypothesis, but without the hypothesis test p-values.

The secondary efficacy endpoint regarding timing of symptom resolution will be analyzed with Kaplan-Meier plots by treatment group.

8.5.2.2 Immunogenicity

Post-baseline antibody titers from ELISA will be compared between treatment groups using ratios of geometric mean titers and associated 95% CIs.

Post-baseline seroconversion from ELISA will be compared between treatment groups using differences in proportions and associated Miettinen and Nurminen 95% CIs.

The summaries listed above will be stratified according to disease status of the subjects.

INO-4800	COVID19-311
Inovio Pharmaceuticals, Inc.	Clinical Protocol

Valid samples for statistical analysis purposes will be those collected within the days of the specified visit according to the Schedule of Events. Baseline is defined as the last measurement prior to the first treatment administration.

The PP population will be used for immunogenicity analyses.

8.5.3 SAFETY ANALYSES

8.5.3.1 Adverse Events

All AEs including injection-site reactions will be summarized among the Safety Population by frequency per treatment arm. These frequencies will be presented overall and separately by dose, and will depict overall, by system organ class and by preferred term, the percentage of subjects affected. Additional frequencies will be presented with respect to maximum severity and to strongest relationship to Study Treatment. Multiple occurrences of the same AE will be counted only once following a worst-case approach with respect to severity and relationship to Study Treatment. All serious AEs will also be summarized as above.

The main summary of safety data will be based on events occurring within 30 days of any dose. For this summary, the frequency of preferred term events will be compared between study arms with risk differences and 95% confidence intervals, using the method of Miettinen and Nurminen. As this analysis will use many event categories, and produce many confidence intervals, caution should be exercised when interpreting these confidence intervals. Separate summaries will be based on events occurring within 7 days of any dose and regardless of when they occurred.

The analyses listed above will also be performed on the subset who are assigned to complete the 7-day post-dose diary. For AE data, partial start dates will be imputed to the date of treatment to conservatively report the event as treatment-emergent, whenever the portion of the date is consistent with that of the study treatment. Otherwise, it will be imputed to the earliest date consistent with the partial date. A completely missing onset date will be imputed as the day of treatment. Partial stop dates will be assumed to be the latest possible day consistent with the partial date.

AE duration will be calculated as (Stop Date – Start Date) + 1.

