7.9 SAFETY DATA REPORTING PERIOD, METHOD OF COLLECTION AND SUBMISSION

All AEs will be collected from the time informed consent is obtained through Day 56. MAAEs, AESIs and SAEs only will continue to be collected after the Day 56 visit and will be followed to resolution or stabilization. This information will be captured in the CRF.

INO-4800	COVID19-311
Inovio Pharmaceuticals, Inc.	Clinical Protocol

If the PI determines that the AE meets serious criteria, then the AE will be recorded as an SAE.

SAEs and AESIs will be reported to the Sponsor from the time the subject signs the informed consent until the last visit.

All SAEs (regardless of causal relationship) and AESIs will be reported on the SAE Report Form and submitted to the Sponsor within 24 hours of becoming aware of the event. The SAE Report Form will be either emailed to [contact] or faxed to The original SAE Report Form must be kept at the clinical trial site.

The event will be data entered into the CRF.

For the events that are considered an AESI, the PI will contact the Sponsor within 24 hours of becoming aware of the event to discuss whether dosing should continue.

Table 11: SAE Contact Information

Sponsor Safety Email: [contact]
Sponsor Safety Fax:
Sponsor Safety Phone:

Table 12: Medical Monitor Direct Contact Information

Primary point of contact, ICON Medic	al Monitor: , M.D.
Email:	
Cell Phone:	
Inovio Medical Monitor:	Jr., M.D., FACP, FIDSA
Email:	
Cell Phone:	

All SAEs, treatment-related AEs, MAAEs and AESIs must be followed by the PI until resolution or return to baseline status, stabilization of the event (i.e., the expectation that it will remain chronic), even if it extends beyond the clinical trial reporting period or until it is determined that the subject is lost to follow up.

Follow-up information is to be submitted to the Sponsor on an SAE Report Form and within 24 hours of becoming aware of the information.

If medical records are submitted to the Sponsor with the SAE Report Form, the clinical trial site must:

- Redact the medical records of all personal data (e.g., confidential subject data, Personal Identifying Information [PII])
- Provide the subject's assigned identification number (SID) on the records

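### The AE start-date imputation rule ignores the recorded stop date, so an event that ended before dose 1 can be counted as treatment-emergent with a zero or negative duration

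*Protocol*

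**What the plan says.** Protocol v2.0, Section 8.5.3.1 (Adverse Events), fixes how incomplete AE dates are handled; v1.0 has the same wording.

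- Partial start: "partial start dates will be imputed to the date of treatment to conservatively report the event as treatment-emergent", but only "whenever the portion of the date is consistent with that of the study treatment". A partial start that does not match goes to the earliest date it allows.
- No start date: "A completely missing onset date will be imputed as the day of treatment". No condition is attached.
- Partial stop: "Partial stop dates will be assumed to be the latest possible day consistent with the partial date".
- Duration: "AE duration will be calculated as (Stop Date – Start Date) + 1".

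The same section defines the tables that these dates feed: "The main summary of safety data will be based on events occurring within 30 days of any dose", and "Separate summaries will be based on events occurring within 7 days of any dose and regardless of when they occurred". Frequencies are also shown separately by dose.

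Section 7.9 sets the collection period: "All AEs will be collected from the time informed consent is obtained through Day 56". The Schedule of Events allows screening up to 30 days before Day 0. Section 5.2 gives two treatment dates, Day 0 and Day 28 (±3 days).

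**The concern.** Moving an uncertain onset to the dosing day is a cautious convention when the event could have begun after dosing. It is not caution when the stop date on the same record shows that the event was over before the first dose. The rule has no step that uses this information.

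Two kinds of output are affected. Event counts in the 7-day, 30-day and by-dose tables can include events that cannot be treatment-emergent. Durations can come out at zero or below, which is impossible for an event that occurred.

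The rule also speaks of one treatment date although each subject has two. When both doses fall in the known month, or when the start is missing altogether, two programmers could assign the same event to different doses.

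**Working it through.** The plan gives no figure to reproduce, so the check applies its rules literally.

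**General case.** Let an event stop on study day s, with s from −30 to −1, and let its start be imputed to Day 0. Duration = s − 0 + 1, which runs from −29 (s = −30) to 0 (s = −1). It is never positive.

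**Illustrative records** (dates assumed):

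| Dose 1 | Start as recorded | Stop | Imputed start | Stop − Start + 1 | Treatment-emergent? |
|---|---|---|---|---|---|
| 25 March | March, day unknown | 10 March | 25 March | 10 − 25 + 1 = −14 | yes, wrongly |
| 25 March | March, day unknown | 24 March | 25 March | 24 − 25 + 1 = 0 | yes, wrongly |
| 20 Sept 2020 | missing | 5 Sept | 20 Sept | 5 − 20 + 1 = −14 | yes, wrongly |
| 20 Sept 2020 | 2020 only | 28 Aug | 20 Sept | −23 + 1 = −22 | yes, wrongly |
| 20 Sept 2020 | missing | Aug 2020, set to 31 Aug | 20 Sept | −20 + 1 = −19 | yes, wrongly |
| 20 Sept 2020 | Aug 2020 | 5 Sept | 1 Aug | 35 + 1 = 36 | no, correctly |
| 20 Sept 2020 | Sept 2020 | Sept 2020, set to 30 Sept | 20 Sept | 30 − 20 + 1 = 11 | yes, defensible |

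The five wrong records all land on the dosing day, so they enter both the 7-day and the 30-day table. The last two rows mark the limits of the problem: a start month without a dose is not moved to the dosing day, and a partial stop in the dosing month gives a positive duration.

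**Which dose.** Take dose 1 on 1 March, dose 2 on 29 March, a start of unknown day in March and a stop on 12 March. Read as dose 1, the duration is 12 − 1 + 1 = 12 days, which is plausible. Read as dose 2, it is 12 − 29 + 1 = −16 days. The text does not choose between them.

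**Grid.** Assume a dose on each day of a 30-day month, onset 1 to 30 days before it, a true duration of 1 to 5 days, and a complete stop date before dosing. This gives 4200 records.

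- Start day missing: 1895/4200 = 45% become treatment-emergent with duration 0 or less (1760 of them negative). The other 2305 are handled correctly.
- Start fully missing: 4200/4200 become treatment-emergent (4050 negative, 150 zero).
- With a check against the stop date: 0 in both settings.

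These shares describe the rule under assumed dates. They do not forecast how often the problem will occur.

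**The case against.** - **The text may be superseded.** The rule is in v2.0. The file also holds v3.0, whose contents list a safety analysis section, but that text is not shown. This stands: the point applies to the latest statistical text available, and persistence in v3.0 cannot be confirmed.
- **It could be left to a separate analysis plan.** Section 8.1 of v2.0 states that the formal plan is contained in Section 8 itself. The point also concerns a rule that is stated and gives a wrong result, not a detail left out.
- **It needs a rare combination.** The start must be incomplete while the stop is known to fall before dosing, and a partial start must also match a dose date. AEs are asked about at Screening, before dosing on Day 0, and by telephone on Days 7 and 35, with a diary in about 500 subjects. This stands as a limit on size.
- **Little depends on it.** No endpoint uses AE duration, and the rule works the same way in both arms. It can inflate per-arm frequencies and add noise to the risk differences, but it has no built-in direction. This also stands.
- **The rule is declared conservative.** That is a fair defence when timing is unknown. It does not cover an event whose own stop date rules out onset after dosing.

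**Conclusion.** The point holds as a minor correction. Applied as written, Section 8.5.3.1 of v2.0 can classify an event as treatment-emergent although its recorded stop precedes dose 1, and the resulting duration is then zero or negative. It also leaves open which dose is the reference.

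This rests on three things in the documents: collection from consent, a screening period of up to 30 days, and no comparison of the imputed start with the stop. The documents give no rate of incomplete dates, so the number of affected events cannot be estimated. It is probably small.

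A reader might infer more than the text supports:

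- **That every partial start is moved to a dosing day.** The matching condition prevents this. Only fully missing starts are always moved.
- **That undated events will accumulate in the 7-day table.** They can enter it, but nothing in the documents indicates how many.
- **That the between-arm comparison is biased.** The rule is the same in both blinded arms.
- **That events will be assigned to the wrong dose.** The text is ambiguous, and the impossible result in the two-dose example arises only if dose 2 is chosen.

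**What to change.** Add to Section 8.5.3.1, or confirm that the current version already contains:

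1. An imputed start may not be later than the known or imputed stop date.
2. If the stop is before dose 1, the event is not treatment-emergent. Its start is the earliest date consistent with what is known, but not before consent.
3. Otherwise, including for ongoing events, use the first treatment date that is consistent with the partial date and not after the stop. If no dose meets both conditions, keep the existing fallback to the earliest consistent date.

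In the first record of the table, with consent assumed on 2 March, the start becomes 2 March, the duration 10 − 2 + 1 = 9 days, and the event is no longer treatment-emergent.

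The cost is a few sentences and one programming condition, with a small downside. When both doses are consistent, choosing the first is a convention and will be wrong for some events. With doses on 1 and 29 March, a true onset on 30 March would be placed 30 − 1 = 29 days early. Choosing the latest dose only reverses the error: with a stop on 5 April, a true onset on 3 March would be placed on 29 March, 29 − 3 = 26 days late.

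Undated events with a stop after dosing will still fall on a dosing day. Flag them, or repeat the 7-day table without them.

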8.5.3.2 Vital Signs

Measurements for vital signs as well as changes from baseline will be summarized with descriptive statistics: mean, standard deviation, minimum, median, and maximum values by time point and treatment arm, for the Safety population. Baseline is defined as the last measurement prior to the first treatment administration.

8.5.4 **DISPOSITION**

Disposition will be summarized by treatment arm for the ITT population and will include the number and percentage randomized, the number and percentage who received each dose and the number who completed the trial. The number and percentage of subjects who discontinued will be summarized overall and by reason. The number in each analysis population will also be presented.

8.5.5 DEMOGRAPHIC AND OTHER BASELINE CHARACTERISTICS

8.5.5.1 Demographics

INO-4800	COVID19-311
Inovio Pharmaceuticals, Inc.	Clinical Protocol

Demographic data will be summarized with descriptive statistics: mean standard deviation, minimum, median, and maximum values for continuous variables, and percentages for categorical variables, by treatment arm, for the ITT and PP populations.

8.5.5.2 Medical History

The percentage of subjects with abnormal medical history findings will be summarized by body system, by treatment arm, for the ITT and PP populations.

8.5.5.3 Prior Medications

Prior medications are those that were used before the start of the trial (prior to Day 0). Partial stop dates of prior medications will be assumed to be the latest possible date consistent with the partial date; start dates will not be imputed. Data for all prior medications will be summarized with percentages by treatment arm, for the ITT and PP populations.

8.5.6 INTERIM ANALYSES

For safety issues or evidence of poor efficacy, the DSMB could recommend stopping enrollment at any time; no formal interim analysis will be performed for this purpose. The two-sided type I error of 0.05 will not be adjusted for possible early stopping due to futility.

8.5.7 MULTIPLICITY

Not applicable; there is one hypothesis that will be tested.

8.5.8 MISSING VALUES

Missing data will not be imputed.

For the ITT analyses of efficacy, subjects with missing or unevaluable data regarding case definition will be considered cases (failures).

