8.5.8 MISSING VALUES

Missing data will not be imputed.

For the ITT analyses of efficacy, subjects with missing or unevaluable data regarding case definition will be considered cases (failures).

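### The supportive ITT efficacy analysis counts missing case data as COVID-19 cases; at a 3.7% attack rate this would largely measure missingness if it covers subjects lost to follow-up

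*Protocol*

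**What the plan says.** Section 8.5.8 of version 2.0 first sets a general rule, "Missing data will not be imputed", and then adds: "For the ITT analyses of efficacy, subjects with missing or unevaluable data regarding case definition will be considered cases (failures". Version 1.0 has the same sentence. Neither version limits it by arm, by reason for missingness or by length of follow-up.

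Section 8.5.1 describes the ITT analysis: "The ITT population will also be used for a supportive analysis counting cases starting from randomization". It also fixes the primary analysis: "The PP population will be primary for the analysis of efficacy in this trial". The same section defines the follow-up time behind k. A case is followed to the date of first diagnosis. A non-case is followed to the date of last follow-up, counted from the "date of the start of surveillance period +1 (for subjects who are non-cases".

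Section 8.6 gives the planning figures: 160 cases, 6178 subjects, a 3.7% attack rate and a true VE of 60%. Section 3.0 of version 3.0 repeats them for the Phase 3 segment.

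**The concern.** Counting missing as failure is familiar for common binary outcomes. Here the event is rare: 3.7% on placebo and, at 60% efficacy, 1.48% on vaccine. Assigning it with certainty to anyone without case data adds nearly the same large number to both arms, which pulls the ratio towards one. If the arms lose different proportions, the difference in loss enters the estimate directly.

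The rule also does not fit the method it feeds. Section 8.5.1 already handles subjects who leave without a case, by ending their follow-up at last contact. A case created by missingness has no diagnosis date, so Section 8.5.1(a) cannot give its person-time and k cannot be computed as written.

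The per-protocol population drops subjects after randomisation for missed doses, protocol violations and early disease. The ITT analysis is the natural check that those exclusions have not distorted the result. At stake is whether it can serve as that check.

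**Working it through.** **Inputs.** From Sections 8.5.1 and 8.6: 3089 per arm, 3.7% attack rate, true VE 60%, margin 30%, one-sided 0.025, exact conditional binomial with Clopper-Pearson limits. Assumed: the missing proportion m (the documents give none), and k = 1, because k is undefined for imputed cases.

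**Reproducing the plan.** With k = 1 the null proportion is 0.70/1.70 = 0.4118 and the alternative is 0.40/1.40 = 0.2857. At 160 cases the critical value is 53 vaccine cases, exact one-sided error is 0.0224 and power is 0.912. The sample size is 2 × 160/(0.037 × 1.4) = 6178, so 3.7% is the placebo-arm rate: 114.3 placebo plus 45.7 vaccine cases.

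**Applying the rule.** With all missing subjects counted as cases:

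- Placebo cases = 3089 × [(1 − m) × 0.037 + m]
- Vaccine cases = 3089 × [(1 − m) × 0.0148 + m]
- VE = 1 − vaccine/placebo

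| m, both arms | Vaccine / placebo cases | Imputed / true | VE | 95% CI |
|---|---|---|---|---|
| 0% | 45.7 / 114.3 | 0 / 160 | 60% | 42.7 to 72.0 |
| 1% | 76.2 / 144.0 | 62 / 158 | 47% | 29.8 to 60.6 |
| 2% | 106.6 / 173.8 | 124 / 157 | 39% | 20.8 to 51.9 |
| 5% | 197.9 / 263.0 | 309 / 152 | 25% | 9.1 to 37.7 |
| 10% | 350.0 / 411.8 | 618 / 144 | 15% | 1.8 to 26.5 |

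**Break-even.** Imputed equals true when m = 0.0259/(1 + 0.0259) = 2.5%, about 156 subjects. The point estimate falls below 30% at m = 3.6%, about 220 subjects. By simulation, the chance that the ITT lower limit exceeds 30% falls from 91% with nothing missing to 49% at 1%, 17% at 2% and 0.2% at 5%.

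**Unequal missingness (vaccine vs placebo).** With true VE 60%, 6% vs 5% gives VE 13%, 5% vs 6% gives 32%, and 12% vs 10% gives 0%. With no true effect, 5% vs 10% gives (0.95 × 0.037 + 0.05)/(0.90 × 0.037 + 0.10) = 0.639, an apparent VE of 36%. The rule is therefore not reliably conservative.

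**Longer ITT window.** Scaling the attack rate to counting from randomisation, 3.7% × 393/351 = 4.1%, gives VE of 40%, 26% and 16% at 2%, 5% and 10% missing. The conclusion does not change.

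**With censoring instead.** If loss is unrelated to risk and lost subjects contribute no cases, expected VE stays at 60%. At 5% missing there are 43 vs 109 cases (CI 43% to 73%); at 10%, 41 vs 103 (CI 42% to 73%).

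**The case against.** The strongest reply concerns whom the rule covers. The case definition needs a positive RT-PCR plus a symptom, so the phrase fits a symptomatic subject with no valid PCR result, while early leavers are already dealt with in Section 8.5.1(b). On that reading few subjects are affected: an illustrative 0.25% or 0.5% per arm gives VE of about 56% or 53%. This is dilution, not collapse. The reading is possible, but the text does not state it, and a subject lost early plainly lacks case data too. The ambiguity itself needs resolving.

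A second reply is that a worst-case rule in a supportive analysis is a recognised stress test. With equal missingness it does pull VE towards zero, but with unequal missingness it need not. No particular imbalance is predicted by the documents: both arms receive the same blinded procedure, so the unequal scenarios only illustrate direction.

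A reader might also infer that Section 8.5.8 flatly contradicts itself. The two sentences can be read as a general rule with a stated exception, so that charge is not needed. The conflict with the person-time definition in Section 8.5.1 stands without it.

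**Conclusion.** The point holds for a supportive analysis. On the natural reading, and under the assumed missingness of 1% to 10% per arm, the ITT estimate would drop from 60% to between about 47% and 15%, and it would move with any difference in loss between arms. Independently of any dropout assumption, follow-up time is undefined for imputed cases.

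A reader might infer that the trial's conclusion is at risk. The documents do not support that. The criterion "Success will be concluded if the one-sided p-value is <0.025" belongs to the primary analysis, which uses the per-protocol population, so its type I error, power and success rule are unchanged. Nor is every broad check lost. The mITT analysis takes everyone with at least one dose, as randomised, and the rule does not reach it. Because randomisation takes place at the Day 0 dosing visit, mITT and ITT should contain nearly the same people, and the two could diverge merely because of this rule.

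It also cannot be said that the current protocol contains the rule. Version 3.0 lists a section on missing values and its change summary describes Phase 3 as mostly as before, but its Section 8 is not in the file. Severity: should-fix.

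**What to change.** First check whether the sentence survives in Section 8.5.8 of version 3.0 and in any separate SAP. If so, replace it along these lines: in the ITT efficacy analysis, subjects without a confirmed case contribute person-time from the start of surveillance to last follow-up and are censored there, using the exact conditional method of Section 8.5.1. State separately how a symptomatic episode without a valid RT-PCR result is classified.

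If a missing-data stress test is wanted, specify it as a sensitivity analysis. Either impute events over the lost follow-up at the placebo-arm incidence (reference-based), or vary the imputed incidence by arm until the conclusion changes (tipping point). No change to mITT is needed on this account.

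The cost is one replaced sentence, a short definition and, if wanted, one sensitivity analysis. Sample size and the primary test do not change. It should be done before unblinding, because a later change would look data-driven.
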